1.0 Background & Rationale

Oppositional defiant disorder (ODD) and conduct disorder (CD), collectively known as disruptive behavior disorders (DBDs), involve persistent physical or verbal confrontations, antisocial behavior, and emotional outbursts. Despite a range of biological and environmental risk factors for DBD, social-cognitive impairments are a common link, and improving these deficits should be beneficial for all patients with DBD.

Children and adolescents with DBD have deficits in social perspective taking that contribute significantly to these behavior problems.^{1, 2} Perspective taking is the ability to perceive the world from another person's point of view,³⁻⁶ including making inferences about the capabilities, feelings, and expectations of others.^{7, 8} It is often measured via self-report measures such as the Perspective Taking subscale of the Interpersonal Reactivity Index.⁹

Perspective taking requires substantial motivation and cognitive resources and can be difficult to achieve, particularly for children.^{10, 11} A failure to understand or value another person's perspective inhibits helping behavior without clear direct benefits.^{12, 13} Perspective taking skills are related to empathic concern, which encompasses feelings of sympathy and concern for unfortunate others,¹⁴ and theory of mind, the ability to accurately infer others' mental states, such as intentions.^{15, 16} Negative attribution biases are more likely in individuals with poor theory of mind.^{15, 17} Thus, improving children's perspective-taking skills should allow them to better understand a counterpart's thinking and intentions, increasing empathic concern, and reducing hostile attribution biases—and therefore improving the likelihood that prosocial behavior occurs.

In the brain, perspective taking engages circuitry underlying empathic concern and theory of mind. In fMRI studies, imagining pain to the self or other, often in conjunction with images depicting painful scenarios, engages a network of regions including anterior insula, dorsal anterior cingulate cortex (dACC), somatosensory cortex, supramarginal gyrus, and amygdala.¹⁸⁻²² A meta-analysis by Lamm et al.²¹ detected that dACC and bilateral anterior insula, the regions most commonly activated in response to other's pain, also show strong responses to self-perspective pain. However, in youth with DBD, there is a decreased response to other-perspective pain in dACC and anterior insula, despite no change or a heightened response to self-perspective pain.²³⁻²⁵

Current treatments to address DBD include a range of pharmaceutical options, one-on-one therapies, and extended prevention programs. For instance, outpatient therapy options include parent management training, which focuses on parent-child interactions, and cognitive-behavioral therapies that specifically target emotion regulation and social problem-solving.^{26, 27} Strategies to improve children's social perspective taking include social skills training, video modeling, acting classes, role-playing, mindfulness training, and parental conversational techniques.^{2, 4, 28-38} However, these strategies often require continued engagement, motivation, and interest from children, and they can be difficult to implement in a self-directed or individualized manner.

To address these concerns, software interventions have shown some promise to improve perspective taking. In a recent adult study,³⁰ users could inhabit the first-person perspective (via a computer screen) of a negotiation counterpart by experiencing parts of their day. This

alternative perspective was found to improve perspective taking and result in more equitable conflict resolution relative to text instructions or other ways of learning about the counterpart. With virtual reality (VR), research in adults has found that inhabiting the virtual body of a member of a specified outgroup reduces stereotypes and increases positive feelings for the elderly,³⁹ different races,⁴⁰ and patients with schizophrenia⁴¹ or colorblindness.⁴² Enacting long-term cognitive or behavioral changes is difficult in children with DBD, and we do not expect small doses to have an extended long-term impact. However, our hope is that extended VR software packages can be developed to work over the long-term, likely in conjunction with more traditional therapy strategies.

VR has exciting therapeutic potential to address perspective-taking deficits because it provides naturalistic yet controlled environments in which users can experience interactions from multiple viewpoints. VR interventions typically provide better generalization to real-world behavioral changes compared to traditional methods.⁴³ VR has an advantage over traditional interventions because it provides an embodied experience that is a middle ground between therapy room settings and the real world (e.g., school, home) where problematic behaviors occur. Our own preliminary data with a VR school cafeteria environment indicates that children find VR to be enjoyable and easy to use, and it invokes real-world reactions—youth with greater conduct problems interpreted encounters with virtual counterparts as more hostile.

In this investigation, we will build upon our current VR design using an Oculus Quest virtual reality headset. After experiencing virtual interpersonal conflicts, subjects will re-experience scenarios in one of two manners: an enriched perspective from the virtual counterpart's point-of-view, with internal dialogue and background information; or a control perspective, which replays the original point-of-view. During this proof-of-concept phase, our primary target is social perspective taking. We will assess functional engagement of this target by quantifying (1) the ability to recognize and understand the virtual counterpart's perspective; and (2) the neural response (in pain circuitry) to pain experienced by the virtual counterpart, a common marker for perspective taking that is abnormal in DBD.^{23, 24, 44}

Medical Device:

The Oculus Quest virtual reality headset will be categorized as a medical device for this investigation. Oculus Quest is commercially available for use by all ages and does not present any serious risks to the health, safety, or welfare of subjects. The headset is a standalone device with goggles and headphones that is used outside the laboratory for both educational and entertainment purposes (for video games, movies, sporting events, etc.). It is similar to other commercially available VR headsets. When using the Oculus Quest, visual stimuli are presented via the goggles along with corresponding sounds. With this investigation, we will program software to present virtual scenarios to participants for short periods at a time (<3 minutes). A minority of participants may experience VR sickness during their experience, which is similar to motion sickness (e.g., mild nausea or lightheadedness). These effects are temporary and dissipate soon after removing the headset, which can be easily done at any time. In addition, these effects are no different than could be experienced if the participant was using the headset outside the laboratory for entertainment purposes.

2.0 Objectives

To investigate the impact of virtually experiencing alternative perspectives on social perspective-taking mechanisms, we will target the following specific aims in youth aged 9-12 who have been diagnosed with a disruptive behavior disorder.

Aim 1: To determine if experiencing alternate perspectives within a VR scenario (with internal dialogue and background context) engages social perspective-taking processes in youth with disruptive behavior disorders.

Aim 2: To evaluate whether VR perspective-taking scenarios increase neural sensitivity to pain experienced by virtual counterparts.

3.0 Outcome Measures

Primary Outcome Measure: VR Perspective Taking Scale

This scale measures the degree to which participants understand the perspective of their virtual counterpart. It will be completed after each VR scenario, both pre- and post-intervention. Each participant's change score will be as Post-treatment (Endpoint; following all VR) vs. Pre-treatment (Baseline; after first scenario). The Cohen's d effect size will be calculated using the difference in mean change scores between treatment and control conditions (e.g., $[\text{Mean}_{\text{Enriched Post-Pre}} - \text{Mean}_{\text{Control Post-Pre}}] / \text{SD}_{\text{pooled}}$), resulting in an effect size measurements for both scales with each treatment condition.

Primary Outcome Measure: Acknowledgement of Other Perspective Scale

This scale allows participants to rate the relative importance of the virtual counterpart's perspective with a scenario-specific question. It will be completed after each VR scenario, both pre- and post-intervention. Each participant's change score will be as Post-treatment (Endpoint; following all VR) vs. Pre-treatment (Baseline; after first scenario). The Cohen's d effect size will be calculated using the difference in mean change scores between treatment and control conditions (e.g., $[\text{Mean}_{\text{Enriched Post-Pre}} - \text{Mean}_{\text{Control Post-Pre}}] / \text{SD}_{\text{pooled}}$), resulting in an effect size measurements for both scales with each treatment condition.

Primary Outcome Measure: Neural response to Self vs. Other Pain

This is an fMRI measure of brain function while imagining pain happening to oneself or the virtual counterpart. Following standard preprocessing of fMRI data, we will calculate the regression coefficient for each stimulus type (Self Pain; Self No Pain; Other Pain; Other No Pain). We will extract mean activity from a priori regions-of-interest (ROIs), established as 10-mm radius spheres around MNI coordinate peaks in dACC (-2,33,40) and anterior insula (left: -40,22,0; right: 39,23,-4), which were identified as key regions for pain response in a recent meta-analysis. Brain activity will be quantified by contrasting self-perspective pain (Self Pain vs. Self No Pain) with other-perspective pain (Other Pain vs. Other No Pain). Cohen's d effect size will be calculated separately for each treatment and each ROI. For more traditional statistical measures, a 2x3 (pain perspective condition by group) within-subjects ANOVA test will be performed on data from each ROI.

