5.0 Study Design

This project will examine how levels of a virtual reality treatment that provides users with the alternate perspective of an interpersonal interaction impacts psychological and neurobiological markers of perspective taking. Prior to Visit 3, participants will be randomly assigned to different VR perspective conditions, stratified by sex, presence/absence of ADHD diagnosis, and ODD/CD diagnosis, via an a priori randomization chart. An equal number of youth will be randomly assigned to either the alternate perspective condition or control condition. Assignment will be sealed for the experimenter until immediately prior to Visit 3 (for visit preparation, experimenter must be unblinded). Visits 1 and 2 will be identical for both groups. At Visit 3, the initial VR scenarios and assessments will be identical. The participant will then re-experience the VR scenarios depending on their assigned condition. Additional VR assessments and the MRI scan will be identical for both groups.

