12.0 Statistical Considerations

We will enroll 95 children in order to target 40 completers ($n = 20/\text{group}$, allowing for 15-20% screen fail and 15-20% attrition). Attrition (apart from screen fails) will occur between the two scanning visits, which are only one week apart and are expected to be due to noncompliance or in-scanner subject motion that renders data unusable. Attrition rates are not expected to

change from year to year, as subjects will remain active only from the time of screening to Visit 3 (up to 8 weeks).

In similar research, pre/post correlations of 0.72 and 0.89 were found for measures of Theory of Mind (closely related to social perspective taking) in a VR intervention for social cognition training.⁵⁰ In research by co-I [name] involving a multi-session skill-building intervention,⁵¹ pre/post scores had a correlation of 0.69 on the Perspective Taking subscale of the Interpersonal Reactivity Index. Here, we use a more conservative estimate for a pre/post correlation of social perspective taking of 0.6. With 20 subjects per group and assuming an ANCOVA model (specified below) is used with a pre/post correlation for social perspective taking of 0.6 an effect size of 0.73 (observed for the meanness rating in the preliminary study) can be detected between two groups with 80% power using a two-sided two-sample t-test with alpha level of 0.05.

For each primary outcome measure, a separate linear mixed model will be employed to determine predictors of post-treatment scores, with pre-treatment scores, condition, time, group, and a time-by-condition interaction term as regressors. Time-by-condition is a regressor to account for potential improvements in perspective taking with treatment (since there are two conflict scenarios presented). From this model, using appropriate contrast statements we can both test for the primary endpoint (change at end of Scenario 3) and examine trends over time between the three groups. We will also conduct with fMRI data a 2x3 (pain perspective condition by group) within-subjects ANOVA on data from each ROI.

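### For both VR scales, the Cohen's d in Section 3 is an unadjusted change-score effect over an undefined SD, while Section 12 powers and tests a baseline-adjusted effect.

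*Combined protocol and SAP*

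**What the plan says.** Section 3.0 (Outcome Measures) uses the same text for the VR Perspective Taking Scale and the Acknowledgement of Other Perspective Scale. Each child's change score is "Post-treatment (Endpoint; following all VR) vs. Pre-treatment (Baseline; after first scenario"). Cohen's d is then "calculated using the difference in mean change scores between treatment and control conditions", with SD_pooled as the denominator. The section does not say whether SD_pooled is the SD of the raw scores or of the changes. It states no baseline adjustment and names no test for these two scales.

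Section 12.0 (Statistical Considerations) bases sample size on a different quantity. The calculation is made "assuming an ANCOVA model (specified below) is used with a pre/post correlation for social perspective taking of 0.6", and it concludes that "an effect size of 0.73 (observed for the meanness rating in the preliminary study") is detectable "with 80% power using a two-sided two-sample t-test with alpha level of 0.05". The analysis it then describes for each primary outcome is a linear mixed model for the post-treatment score with the pre-treatment score among the regressors. The primary endpoint is tested by contrasts from that model and is described there as the change at the end of the third scenario.

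Neither section says whether the Section 3.0 d or the Section 12.0 contrast is the headline effect for Aim 1.

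**The concern.** A raw difference in mean change and a baseline-adjusted difference are two estimators of the same treatment effect. Under randomisation they have the same expectation, but they differ in precision and in how they respond to chance imbalance at baseline. The plan is sized and tested on the adjusted one, yet the only effect size it defines for these scales is the unadjusted one.

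Three things are at stake. The published d would be noisier than the analysis behind it, and a confidence interval around it could disagree with the model's p-value. With 20 children per arm, chance baseline differences are likely to be noticeable, and raw change handles them poorly. The denominator is also open, so a reader cannot tell whether an observed d is on the same scale as the planning value of 0.73.

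**Working it through.** **Inputs from the documents**
- 20 completers per group, equal allocation: "With 20 subjects per group and assuming an ANCOVA model (specified below) is used" (Section 12.0) and "An equal number of youth will be randomly assigned to either the alternate perspective condition or control condition" (Section 5.0).
- Pre/post correlation r = 0.6: "we use a more conservative estimate for a pre/post correlation of social perspective taking of 0.6" (Section 12.0).
- Effect 0.73, two-sided t-test, alpha 0.05, power 80% (Section 12.0).

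**Assumptions added here**
- Pre- and post-treatment SDs are equal and set to 1.
- 0.73 is in raw-score SD units. The plan does not name the SD, but this reading reproduces its 80%.
- There is one pre and one post score per child, in place of the repeated-scenario model.

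**Step 1. Reproduce the plan's figure.**
ANCOVA residual SD = sqrt(1 − r²) = sqrt(1 − 0.36) = 0.80.
Effective d = 0.73 / 0.80 = 0.9125.
Noncentral t, 20 per group: power 80.3% with 38 df, 80.2% with 37 df. The stated 80% is confirmed.

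**Step 2. Precision of the Section 3.0 quantity.**
SD of raw change = sqrt(2(1 − r)) = sqrt(0.8) = 0.894.
Variance ratio, raw change to ANCOVA = 0.80 / 0.64 = 1.25, so 25% more variance.

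**Step 3. Power if raw change were the tested quantity.**
Effective d = 0.73 / 0.894 = 0.816. Noncentral t with 38 df: power 71.1%.
The d detectable on the analysed scale with 80% power and 20 per group is 0.909. In raw-score SDs this is 0.909 × 0.894 = 0.81 for raw change and 0.909 × 0.80 = 0.73 for ANCOVA. Raw change would need 25 per group for 80% power at 0.73 (80.7%; 24 per group gives 79.0%).

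**Step 4. Dependence on r** (20 per group, effect 0.73, 38 df)

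| r | Raw change | ANCOVA |
|---|---|---|
| 0.4 | 54% | 69% |
| 0.5 | 61% | 74% |
| 0.6 (planning value) | 71% | 80% |
| 0.69 (cited in Section 12.0) | 82% | 87% |
| 0.72 (cited in Section 12.0) | 85% | 90% |
| 0.89 (cited in Section 12.0) | 99.8% | 99.9% |

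**Step 5. Chance baseline imbalance.**
Raw change subtracts the whole baseline difference. With equal SDs the regression slope is r = 0.6, so the excess correction is 1 − 0.6 = 0.4 of the imbalance. The standard error of the baseline difference is sqrt(2/20) = 0.32 SD. One standard error of imbalance therefore shifts the raw-change estimate by 0.4 × 0.32 = 0.13 SD relative to the adjusted one, which is 0.13 / 0.73, or about 17% of the planned effect. Randomisation is stratified by sex, ADHD status and ODD/CD diagnosis, not by baseline score, so it does not control this imbalance directly.

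**Step 6. Scale of d.**
If SD_pooled is the SD of change, a true 0.73 raw-score effect appears as d = 0.73 / 0.894 = 0.82. If it is the raw-score SD, it appears as 0.73.

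**The case against.** The strongest reply is that Section 3.0 gives an effect-size formula and no test. A formula has no power of its own. The inference is set out in Section 12.0, where the baseline score is in the model and the 80% is correct. The fMRI outcome in Section 3.0 is arranged in the same way, with Cohen's d first and a conventional test named separately. This stands. A reader might infer from Section 3.0 that the trial really has 71% power instead of 80%, but the documents do not support that, because they nowhere specify a test on raw change.

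Nor does the Section 12.0 description of the endpoint as a change imply an unadjusted test. With the pre-treatment score as a covariate, modelling the change or the post score gives the identical treatment effect.

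It is also tempting to say that the reported d cannot be compared with 0.73. That holds only if SD_pooled is the SD of change. What the text shows is an undefined denominator, not a proven incompatibility.

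Finally, all three correlations cited in Section 12.0 exceed 0.6, and at each of them even raw change would pass 80% power; the crossing is near r = 0.68. This is fair, but 0.6 is the value the plan chose to rely on.

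None of this removes the mismatch. The d to be reported is still not the effect that is powered and tested, its denominator is still undefined, and the excess noise and over-correction still apply to it.

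**Conclusion.** The point holds as a mismatch between the reported effect and the tested effect, not as an error in the power calculation. The 80% is right for the Section 12.0 analysis under its stated inputs. The Section 3.0 d is less precise: 25% more variance at r = 0.6, and about 0.13 SD of over-correction per standard error of baseline imbalance. The plan does not say which effect is primary or what SD_pooled is.

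The 71% figure is conditional. It applies only if raw change is made the tested analysis, and it rests on r = 0.6, equal pre and post SDs, 0.73 in raw-score units, and one pre and one post score. If 0.73 were already in change-score SD units, power for such a test would be about 61%. These figures approximate the repeated-scenario mixed model and do not evaluate it directly. The issue is worth correcting, but it does not undermine the Section 12.0 test.

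**What to change.** In Section 3.0, for both VR scales:
- State that the primary effect is the baseline-adjusted between-arm contrast from the Section 12.0 model.
- Name the SD that standardises it, for example the pooled baseline SD, and report it with a 95% CI.
- Keep the raw-change d as descriptive, with its own denominator stated.
- In Section 12.0, say which SD the 0.73 refers to.

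Only if the sponsor intends to test the raw change difference as the primary analysis should power be restated, as about 71% with a detectable effect of about 0.81 raw-score SDs.

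The cost is a few lines of wording. No new data are needed: the baseline scores are already collected at Visit 3, and Section 12.0 already adjusts for them.

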Participants will undergo an MRI scan that will last about 1 hour. Prior to the scan, the parent and child will complete the Indiana Institute of Biomedical Imaging Sciences (IIBIS) **MRI Safety Screening Form** to confirm that there are no MRI contraindications. They will also complete the **Medication Log** form to indicate what medications or caffeine the subject had taken that day. This information will also be provided to parents during the reminder call or email for Visit 3, with a request that the same substances be utilized at Visit 3 if possible.

Participants will also see examples of stimuli that they will view during the scan and be instructed on what the MRI task will entail. They will practice button-press tasks as well.

MRI scans will take place on a research-dedicated 3T Siemens Magnetom Prisma MRI scanner at Goodman Hall. First, we will conduct a 3D magnetization prepared rapid gradient echo (MPRAGE) scan for individual anatomical reference, comprised of 160 sagittal slices with 1.0x1.0x1.2 mm voxel dimension. In the scanner, images will be presented via E-prime

software and back-projected to participants. Functional scans will be acquired using T2*-weighted gradient spin echo-planar imaging (EPI) sequence with TR/TE 1200/29 ms for 54 axial slices and voxel size of 2.5x2.5x2.5 mm.

The fMRI task employs a paradigm that has compared self vs. other perspective taking in the response to painful stimuli.¹⁸⁻²¹ A mixed block fMRI design will be used, with two 8-minute runs of our task. There are four conditions: self pain, self no pain, other pain, and other no pain. Each block (40sec duration) will be either "Self" or "Other," as indicated by task instructions prior to the block ("Imagine these situations are happening to you/him/her) and an image of the virtual avatar (virtual self or virtual counterpart; image remains in corner throughout block). Within the block, participants will be shown Pain images (e.g., hand slammed in door) and No Pain images (e.g., hand on door handle) (3 each/block; 2sec duration; jittered interstimulus interval 2-5sec).¹⁸⁻²⁰ There will be 6 blocks of each type during both 8-minute runs (96 total trials/run), with block order pseudorandomized across participants.

An additional task will present subjects with child faces with different emotional faces and ask them to respond to specific questions that probe emotion recognition, empathy, or the sex of the face.

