After the MRI, the subject will be presented with a series of images. They will then determine which of the images they saw while completing the tasks in the MRI. This task measures how well subjects were attending to stimuli during the brain scan.

Visit 3

Participants will take part in the VR task with the Oculus Quest VR headset. We will fit the headgear to the child and ensure that it is comfortable. Subjects will remain seated while interacting with the virtual world and use hand-held controls to move or control objects. Subjects can turn their head to look in any direction in the virtual world. Using state-of-the-art 'Oculus Touch' hand-held controllers that react to hand movements, the user will be able to move and interact with virtual objects and characters. Headphones play auditory stimuli.

Children will first explore the virtual cafeteria for three minutes to allow them to understand hand controls and become acquainted with the environment before starting the task scenarios. They may ask questions and talk with investigators during this time, who will ensure that subjects are able to use controls and move around in the environment properly.

The virtual environment is a school cafeteria setting. Following practice, participants will take part in three scenarios in the school cafeteria. Each scenario will last up to two minutes. In two scenarios, after the subject hears the school bell ring, the goal is to place trash on their cafeteria tray and take the tray to the trash. In a third scenario, the subject is directed to clean up the mess at their table. Once the task is complete, the scenario will be complete. In each scenario, virtual characters will populate the environment to make it more realistic, including some characters (students) who will also be returning their trays. However, the social environments will differ, and each scenario includes a virtual counterpart that interferes with the goal.

After each scenario, children will remove the headset and complete questions via electronic tablet. First, they will complete our **VR Perspective Taking Scale**, which assesses how well they understand the virtual counterpart's perspective. Next, they will complete a question for the **Acknowledgement of Other Perspective Scale**, which reflects the relative importance given to the perspective of the participant and the virtual counterpart.

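### The effect size for the primary fMRI outcome reads as one Cohen's d per arm, not a between-arm difference in change, so the reported d would not estimate the intervention effect

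*Combined protocol and SAP*

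**What the plan says.** Section 3.0 names three primary outcome measures. For each of the two VR scales, "The Cohen's d effect size will be calculated using the difference in mean change scores between treatment and control conditions", and a formula follows: enriched mean change minus control mean change, over the pooled SD.

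For the third, the neural response to self versus other pain, the measure is a within-person contrast: "Brain activity will be quantified by contrasting self-perspective pain (Self Pain vs. Self No Pain) with other-perspective pain (Other Pain vs. Other No Pain". It is taken in three ROIs, at "MNI coordinate peaks in dACC (-2,33,40) and anterior insula (left: -40,22,0; right: 39,23,-4". The effect size is then given in one sentence: "Cohen's d effect size will be calculated separately for each treatment and each ROI". No formula is attached, no scan is named, and neither a control subtraction nor a Visit 2 to Visit 3 change appears.

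Two other fMRI analyses are planned. Section 3.0 adds that "a 2x3 (pain perspective condition by group) within-subjects ANOVA test will be performed on data from each ROI". Section 12.0 says: "For each primary outcome measure, a separate linear mixed model will be employed to determine predictors of post-treatment scores", with pre-treatment score, condition, time, group and a time-by-condition term as regressors.

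Section 5.0 randomises equal numbers to two conditions, alternate perspective and control.

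**The concern.** Aim 2 asks whether the perspective-taking scenarios raise neural sensitivity to the counterpart's pain. An effect size that answers this must separate the assigned condition from everything else that happens between the two scans, and both arms share a good deal of that.

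- In the scanner, each block carries "an image of the virtual avatar (virtual self or virtual counterpart; image remains in corner throughout block". At Visit 2 the child has not yet been through any conflict scenario with that counterpart.
- At Visit 3, before the second scan, every child goes through three scenarios, and "each scenario includes a virtual counterpart that interferes with the goal". Section 5.0 says that these initial scenarios are identical in both arms.
- Both arms then have a second VR run, because the control condition replays the interaction from the child's own viewpoint.
- Both arms repeat the same scan session.

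Any of these could move the response to the counterpart's pain in both arms. The control arm is there to subtract that movement, and a d computed within one arm leaves it in. This is a proof-of-concept study of target engagement, and Section 3.0 presents the ANOVA as the more traditional addition to d. The effect size is therefore a main product of the trial and likely to be carried into later planning.

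**Working it through.** **1. The plan's own figure.** Section 12.0 states 80% power for an effect size of 0.73 with 20 per group, ANCOVA, pre/post correlation 0.6 and two-sided alpha 0.05.
- Residual SD: √(1 − 0.6²) = 0.8, so the adjusted standardised difference is 0.73/0.8 = 0.9125.
- Noncentrality: 0.9125 × √(20/2) = 2.886.
- Power by noncentral t: 80.3% (38 df) or 80.2% (37 df). The normal approximation gives 82.3%.

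The figure reproduces. It is a between-arm figure for social perspective taking. The documents give no corresponding figure, SD or between-scan change for fMRI.

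**2. What each definition estimates.** Let B be the mean Self/Other contrast at Visit 2, C the change shared by both arms, and E the added effect of the alternate perspective. In raw units:

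| Numerator of d | Alternate | Control | Alternate minus control |
|---|---|---|---|
| Visit 3 minus Visit 2 | C + E | C | E |
| Visit 3 alone | B + C + E | B + C | E |

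Only the last column isolates E. Either per-arm reading carries C, and the single-scan reading carries B as well.

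**3. Size, by simulation.** Inputs: 20 per arm (Section 12.0), normal change scores with SD 1, and 100,000 runs per setting. C and E are assumptions, in change-score SDs.

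| C | E | Mean d, alternate | Mean d, control | Mean between-arm d |
|---|---|---|---|---|
| 0 | 0 | 0.00 | 0.00 | 0.00 |
| 0.3 | 0 | 0.31 | 0.31 | 0.00 |
| 0.5 | 0 | 0.52 | 0.52 | 0.00 |
| 0.5 | 0.5 | 1.04 | 0.52 | 0.51 |

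The averages slightly exceed the true values because the sample d is biased upwards in small samples. With no intervention effect, the between-arm test rejected in 5% of runs whatever the value of C.

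**4. Precision at 20 per arm** (approximate 95% half-widths).
- Within one arm, at d = 0.45: 1.96 × √(1/20 + 0.45²/40) = 0.46.
- Between arms, near d = 0: 1.96 × √(2/20) = 0.62.

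**The case against.** **The arms are compared elsewhere.** A reader might infer that the plan never tests the arms against each other on fMRI, or that it discards the control arm. The documents do not support this. The fMRI measure is headed as a primary outcome, and Section 12.0 fits a mixed model with pre-treatment score and condition to each primary outcome, so change shared by both arms falls outside the condition contrast. This objection stands and limits the point to the effect size. It does not remove it, because the model is not said to produce d. The ANOVA is a weaker substitute: it names no time factor and has three group levels for two randomised arms.

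**The sentence may mean each treatment against control.** After giving its between-arm formula, Section 3.0 speaks of effect sizes with each treatment condition. The 2x3 layout and the three groups mentioned in Section 12.0 would fit an earlier design with more than one treatment. On that reading the sentence already intends a between-arm d and is only stale. The text does not settle this. With two arms the plain reading is one d per arm, and a primary effect size should not depend on guessing.

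**False claims from one significant arm.** It is tempting to count how often exactly one arm would look significant with no difference between arms. With p the power of a paired t-test at n = 20, that chance in one ROI is 2p(1 − p):
- 9.5% for no shared change (p = 0.05);
- 37% for 0.3 (p = 0.247);
- 49% for 0.5 (p = 0.565);
- 14% for 0.8 (p = 0.924).

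The arithmetic is right, but no section plans within-arm significance tests. These figures describe a possible misuse of per-arm results, not an error rate of the plan.

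**Conclusion.** The point holds for the effect-size definition and no further. Followed literally, Section 3.0 yields for each ROI a d per arm that is not a treatment effect, and two of the three primary outcomes would have a d with a different meaning from the third. The planned mixed model still compares the arms.

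The size depends on how much both arms change between scans, which the documents do not give. If nothing is shared and d is taken on change, the alternate arm's d is on target. With an assumed shared change of 0.5 SDs, a null intervention shows a d of about 0.52 in each arm, and a true effect of 0.5 shows as about 1.04, roughly double the between-arm value. If d is taken at Visit 3 alone, the pre-existing Self/Other difference is added to this.

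Severity is moderate: the sample size, randomisation, data collection and planned model are unaffected, and the sentence may be a remnant that was meant correctly.

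**What to change.** Replace the sentence in Section 3.0 with: 'For each ROI, Cohen's d is the between-arm difference (Alternate minus Control) in the Visit 3 minus Visit 2 change in the Self/Other pain contrast, divided by the pooled SD, with a 95% CI.' State the direction of the Self/Other subtraction so that the sign of d can be read. Label any per-arm d as descriptive only, noting that it includes exposure to the counterpart and repetition of the task. While editing, reconcile the 2x3 layout and the three-group wording with the two randomised arms.

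The change costs one sentence, with no new data and no change to 20 per group. The downside is a wider interval, about ±0.62 between arms against about ±0.46 within an arm. On change scores with 20 per group, the between-arm d detectable with 80% power is 0.91 change-score SDs, so the fMRI estimate will be imprecise. That is the precision the design gives for the question in Aim 2.
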